6.1.1 Composition

Each vial of JR-171 contains the following ingredients:

Table 6-1 Composition of JR-171 formulation

6.2 Preparation/Handling/Storage/Accountability

6.2.1 Acquisition and Accountability

Detailed procedures for the management of the investigational product are provided in the sponsor's instruction for administration of investigational product in a separate document.

The sponsor will confirm that the study sites are ready to conduct the study, and that the study contract has been concluded with each of them, before delivering the investigational product to the study sites.

Before the investigational product is delivered, the person in charge of managing the investigational product and the study monitor is to check the quantity to be delivered, the manufacturer's serial number, the method of storage, the expiration date, etc. and exchange the required set of documents for the drug release process.

Investigation study sites should manage the investigational product in accordance with the instruction of investigational product (e.g., receipt, handling, and storage instructions) and the Institution's standard operating procedures (SOP). Investigation study sites should register investigational product specific details (regarding receipt, amount used, disposal, etc.) in an Interactive Response Technology (IRT) system.

After the completion of the study, the investigation study site will return any undispensed investigational product with due consideration to the protection of personal information of the subjects.

6.2.2 Product Storage and Stability

6.2.3 Preparation

6.3 Measures to Minimize Bias: Randomization and Blinding This is an open-label trial.

In Part 2, subjects without previous HSCT treatment will be stratified by their phenotype (Scheie or other than Scheie) and randomized into one of the 2 treatment groups (2.0 or 4.0 mg/kg/week JR-171 group) using an IRT system except for subjects who receive JR-171 administration in a dose-escalation manner. Those subjects with previous HSCT treatment will be allocated into a treatment group without stratification by their phenotype. The handling of randomization lists is described in a separate document.

6.4 Study Intervention Compliance

In the JR-171-101 study, the investigational product will be administrated under supervision of the principal investigator or subinvestigator in order to assure compliance with investigational product administration. Site monitors will check subject's compliance with the investigational product administration.

6.5 Concomitant Medication/Therapy

All the concomitant medications/therapies used should be recorded from the initial administration of the investigational product to the end of the study period. For all concomitant medications, the status of use (drug name, route of administration, duration of treatment, and reason for administration) should be recorded in the electronic case report form (eCRF). Transfusions or maintenance transfusions for purpose of establishment an intravenous line, diluents for injections, bases for in-hospital preparations, disinfectants and drugs used in preparative treatments *e.g.*, anesthetic (other than drugs with anticipated effects) are not considered as concomitant medications. For all concomitant therapies, the status of use (therapy name, duration of treatment, and reason for therapy) should be recorded in the eCRF.

6.5.1 Prohibited Concomitant Medications/Therapies

Concomitant use of the following drugs and therapies is prohibited during the period from the screening test to the end of the study period:

- Investigational products other than JR-171
- HSCT

Concomitant use of the following drug is also prohibited during the period from the initial administration of JR-171 to the end of the study period:

Laronidase

For this protocol, a prescription medication is defined as a medication that can be prescribed only by a properly authorized/licensed clinician. Medications to be reported in the eCRF are concomitant prescription medications and over-the-counter medications.

JR-171 Phase I/II study Version 6.00 Protocol number: JR-171-101 12 November 2021

6.5.2 Rescue Medicine

Appropriate medication will be immediately provided to the subject when a principal investigator or subinvestigator deems this to be necessary.

6.6 Dosing and Administration

6.6.1 Confirmation of Safety

Part 1: Doses in Part 1 are 0.1, 1.0, 2.0, 4.0 mg/kg and will be administered to a subject at intervals of 1 week. Considering that this is a first-in-human study of JR-171, the safety of JR-171 will be initially evaluated in four adult MPS I patients aged 18 years or older in Part 1. In Part 1, each subject will stay in the hospital and will be supervised until 21 hours after the end of each administration to assess safety. When the principal investigator or subinvestigator concludes that JR-171 dose increase will pose no problem based on the safety information collected from the administered dose to the first and second subject, JR-171 will be increased to the next dose upon approval of the sponsor.

The sponsor will establish an IDSMC. If any IARs with Common Terminology Criteria for Adverse Events (CTCAE) grade ≥ III occur up to 24 hours after the end of each administration in the first and second subjects, the sponsor will consult with the IDSMC to ask their opinion about the appropriateness of the JR-171 dose increase. The dose increase determination will be made according to the same procedures for each dosage. The start date of JR-171 administration of the second subject should be at least 1 week after the start date of JR-171 administration of the first subject. Once the two subjects complete all the four times of administrations and the safety of JR-171 is confirmed, then the administration for the third and subsequent subjects may be started. If the first or second subject is discontinued from the study during the dose-escalation phase (until the safety evaluation of the fourth administration), the next third subject will stay in the hospital and will be supervised until 21 hours after the end of each administration to assess safety.

After completing the clinical study for all subjects who participated in Part 1, the sponsor will convene the IDSMC and ask their opinion about the appropriateness of the initiation of Part 2 based on all safety data collected from the start of administration to Week 5. After taking into consideration the opinion of the IDSMC, when the sponsor concludes, that initiation of Part 2 will pose no problem, from ethical, scientific, and medical perspective, then Part 2 may be initiated.

Part 2: The first subject aged 6-17 years and the first subject aged 2-5 years (0-5 years in Japan and Brazil) shall each receive an initial dose of JR-171 as an intravenous infusion at a dose of 1.0 mg per kg of body weight. The dose level shall be then increased to 2.0 mg/kg for the second administration, and to 4.0 mg/kg for the third administration. From the fourth to twelfth administrations, JR-171 shall be administered at 4.0 mg/kg. If the first subject aged 6-17 years or the first subject aged 2-5 years (0-5 years in Japan and Brazil) is discontinued from the study during the dose-escalation phase (until the safety evaluation of the third administration), the next subject for the same age group shall receive JR-171 in a dose-escalation manner as described above (the schedule of assessments will also be the same as those for the first subject in each age group).

The first subject aged 2-5 years (0-5 years in Japan and Brazil) can receive the initial administration at least 1 week after the first subject aged 6-17 years receives the initial administration.

Subjects other than the above of aged 2 years or older (any age in Japan and Brazil) shall be allocated to receive either 2.0 or 4.0 mg/kg/week JR-171 group. The safety evaluation in Part 2 will be conducted in subjects aged 2-17 years (0-17 years in Japan and Brazil). The first subject aged 6-17 years will stay in the hospital and will be supervised until 21 hours after the end of each administration at Week 1, Week 2 and Week 3 to assess safety. When the principal investigator or subinvestigator, and the

sponsor confirm the safety in the first subject aged 6-17 years after the end of third administration, the second and subsequent subjects aged 6-17 years can be assigned to either 2.0 or 4.0 mg/kg/week JR-171 group. If any IARs with CTCAE grade ≥ III occur up to 24 hours after completion of the administration among the dose-escalating infusions in the first subject aged 6-17 years, the sponsor should convene the IDSMC and ask their opinion about the appropriateness of the JR-171 dose increase.

The first subject aged 2-5 years (0-5 years in Japan and Brazil) can receive the initial administration at least 1 week after the first subject aged 6-17 years receives the initial administration. The first subject aged 2-5 years (0-5 years in Japan and Brazil) will stay in the hospital and will be supervised until 21 hours after the end of administration at Week 1, Week 2 and Week 3 to assess safety. When the principal investigator or subinvestigator, and the sponsor confirm the safety in the first subject aged 2-5 years (0-5 years in Japan and Brazil) after the end of third administration, the second and subsequent subjects aged 2-5 years (0-5 years in Japan and Brazil) can be assigned to either of 2.0 or 4.0 mg/kg/week JR-171 group. If any IARs with CTCAE grade ≥ III occur up to 24 hours after completion of the administration among the dose-escalating infusions in the first subject aged 2-5 years (0-5 years in Japan and Brazil), the sponsor should convene the IDSMC and ask their opinion about the appropriateness of the JR-171 dose increase.

The sponsor's Safety Evaluation Manual in a separate document will be followed for the confirmation of safety procedure.

6.7 Instructions for Subjects

The principal investigator or subinvestigator must fully inform the subjects about the purpose and significance regarding the clinical study, and must instruct subjects according to the following items.

- Female subject or male subject whose co-partner is of childbearing potential is required
 to refrain from conception during the study period and/or to use an adequate method of
 contraception. The subject or co-partner should contact the principal investigator or
 subinvestigator immediately if they suspect that they might be pregnant.
- 2. The subject and co-partner must be willing to use a medically accepted, highly effective method of contraception, such as spermatocidal gel plus condom, an intrauterine device or oral contraceptives.
- 3. The subject or co-partner must use an adequate method of contraception until one month after the final administration.

6.8 Intervention after the End of the Study

The sponsor is planning an extension study of the Study JR-171-101 of over 5 years' duration to confirm the long-term safety and efficacy of JR-171.

7. Discontinuation of Study Intervention and Subject Discontinuation /Withdrawal

7.1 Discontinuation of Study Intervention

7.1.1 Criteria for Termination or Suspension

The sponsor will consider the discontinuation/cessation of the whole or part of the clinical study in any situation described in the information below. In this case, all principal investigators will be immediately informed by the sponsor.

- 1. Occurrence of a serious adverse event (SAE) with CTCAE grade ≥ IV
- 2. Occurrence of serious adverse drug reactions coded to same preferred term (PT) in 2 or more subjects
- 3. A research report that suggests the tendency of occurrence of adverse drug reactions,

JR-171 Phase I/II study Version 6.00 Protocol number: JR-171-101 12 November 2021

such as the number of reactions that occur, the frequency of occurrence, and occurrence conditions, have significantly changed

- 4. A research report that shows the clinical study may cause serious diseases including cancer, disabilities, or death
- 5. When the clinical study suggests that there is no efficacy of JR-171 in this population
- 6. A research report that demonstrates that there is no efficacy or effectiveness for the disease that the clinical study aims to treat
- 7. When either the sponsor, the study institution, or the principal investigator has committed a grave breach of ICH-GCP, the protocol, or the contract, leading to a situation where the proper continuation of the clinical study is considered problematic
- 8. When the continuation of the clinical study is considered difficult due to changes of the structure or environment for conducting the clinical study (e.g., a transfer of the principal investigator)
- 9. Other cases in which the continuation of the clinical study is considered inappropriate due to new information or a change in the situation identified during the clinical study

When the clinical study is discontinued the following examinations/observations described below are to be performed as much as possible, if the subject agrees, after final administration of the investigational product. The details should be recorded in the eCRF listed below except for items 3, 4, 5, 7 and 9, it is not necessary to record measurements in the eCRF. The date of discontinuation and the reason for discontinuation will also be recorded in the eCRF.

- 1. Vital signs (pulse rate, body temperature, blood pressure, respiratory rate and percutaneous oxygen saturation)
- 2. Laboratory tests (hematologic test, blood biochemical test, determination of serum iron levels, and urinalysis)
- 3. Antibody tests (anti-IDUA and anti-JR-171 antibodies)
- 4. Drug concentration in CSF
- 5. HS and DS concentrations in CSF
- 6. CSF opening pressure
- 7. Urinary HS and DS concentrations
- 8. Urinary creatinine
- 9. Serum HS and DS concentrations
- 10. Liver and spleen volumes
- 11. Cardiac function
- 12. 6-minute walk test (Part 2 only)
- 13. Other clinical findings related to neurocognitive and behavioral changes
- 14. 12-lead electrocardiogram
- 15. AEs
- 16. Concomitant medications/therapies

Note that the items below are very invasive tests and will be conducted only when the principal investigator or subinvestigator deems them possible by considering matters including the condition of a subject and the frequency of lumbar puncture. For items 1 and 2, it is not necessary to record measurements in the eCRF. For the reporting of the results, data should be reported by the laboratory.

- 1. Drug concentration in CSF
- 2. HS and DS concentrations in CSF
- 3. CSF opening pressure

After completion of examinations/observations at discontinuation, the principal investigator or subinvestigator should consider the necessity of (re)starting of laronidase in consideration of the subject's status (e.g., progression to underlying disease or a significant worsening of their clinical parameters including serum and urinary HS and DS concentrations).

7.2 Subject Discontinuation/Withdrawal from the Study

Subjects are free to withdraw from participation in the study at any point of time upon request

JR-171 Phase I/II study Version 6.00 Protocol number: JR-171-101 12 November 2021

to the principal investigator. Subjects who are prematurely withdrawn from the study will not be replaced.

A principal investigator or subinvestigator may discontinue or withdraw a subject from the study for the following reasons:

- 1. When a subject or his/her legal representative wishes to discontinue the clinical study
- 2. When the continuation of the study became impossible for reasons including a transfer to another hospital/change of address during the clinical study
- 3. When a subject was found to be ineligible after the start of the clinical study such that continued participation would compromise safety of the subject or integrity of the study
- 4. When the continuation of the clinical study becomes impossible for reasons including the occurrence of an AE*
- 5. When a subject experiences anaphylactic shock
- 6. Other cases in which the principal investigator or subinvestigator deems it necessary to discontinue the clinical study because compliance with the protocol has become difficult

*When the occurrence of an SAE with CTCAE grade ≥ IV, the principal investigator or subinvestigator should consider the discontinuation/temporary cessation of the study. If the principal investigator or subinvestigator can rule out a causal relationship with JR-171 based on the additional information and CTCAE grade improved to III or less, administration could be resumed, but otherwise subjects must be discontinued.

For examinations/observations at the time of the subject discontinuation from the study, see Section 7.1.1.

7.3 Lost to Follow-up

For subjects who do not visit the hospital, the principal investigator or subinvestigator will inquire into reasons and their subsequent progress and record the information in the eCRF.

Discontinuation of specific sites or of the study as a whole are handled as part of Appendix 1 (see Section 10.1.18).

8. Study Assessments and Procedures

[figure not shown]
- Study procedures and their timing are summarized in the Schedule of Activities. Protocol waivers are not allowed.
- Immediate safety concerns should be discussed with the sponsor immediately upon occurrence or awareness to determine if the subject should continue or discontinue study intervention.
- Adherence to the study design requirements, including those specified in the Schedule of Activities, is essential and required for study conduct.
- All screening evaluations must be completed and reviewed to confirm that potential subjects meet all eligibility criteria. The principal investigator will maintain a screening log to record details of all subjects screened and to confirm eligibility or record reasons for screening failure, as applicable.
- Procedures conducted as part of the subject's routine clinical management (e.g., blood count) and obtained before signing of the ICF may be utilized for screening or baseline purposes provided the procedures met the protocol-specified criteria and were performed within the time frame defined in the Schedule of Activities.

8.1 Demographic and Other Baseline Characteristics

The following will be investigated and recorded in the eCRF:

- Date of written consent obtained from the subject and, if applicable, written permission from his/her legally acceptable representative
- Age at the time of informed consent
- Date of diagnosis of MPS I
- Presence or absence of use of laronidase, and start date (if applicable)

- Presence or absence of HSCT treatment, and treatment date (if applicable)
- Phenotype of MPS I (Hurler, Hurler-Scheie or Scheie)
- Presence or absence of intellectual disabilities
- Presence or absence of MPS I-related/-unrelated concurrent disease (events occurring at the time of informed consent) and, if applicable, the name of these diseases
- Presence or absence of medical history (MPS I-related medical occurrence), and if applicable, the name of any disease
- Enzyme activity in leucocytes or cultured skin fibroblasts and the date of measurement (if applicable)
- Urinary GAG concentration, or uronic acid concentration, and date of the measurement (if applicable)
- Genetic analysis results (for subjects who do not have the result, genetic analysis will be performed during this clinical study)
- Presence or absence of laronidase-related IAR
- Race
- Country
- Sex (as well as ability to get pregnant, if female)
- Inclusion and exclusion criteria

8.2 Safety Assessments

8.2.1 Pregnancy Testing (Female Subjects of Childbearing Potential Only)
Pregnancy testing will be conducted during screening for female subjects of childbearing potential (female subjects of non-childbearing potential are confirmed by being either post-

menopausal for more than 1 year prior to the time of informed consent or surgically sterile). In the eCRF, whether or not a measurement has been performed as well as the sample collection date and results of measurement, if performed, should be recorded.

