1.3 Schedule of Activities

Part 1

Observation/test timing	Pre-screening	Screening test	Registration	Baseline	Week 1	Week 2	Week 3	Week 4	Week 5	Discontinuation
Visit window	-	28 days before Day 1 (Day -28) to Day -7	-	Day -2 to Day 1	Day 1	Day 8 to Day 11	Day 15 to Day 18	Day 22 to Day 25	Day 29 to Day 32	Within 28 days from discontinuation
JR-171 administration					Х	Χ	Х	Χ		
Informed consent	X									
Subject baseline characteristics ^{a)}		Х								
Assessment based on			Х							
inclusion/exclusion criteria			^							
Pregnancy testing (female subjects of childbearing potential only)		X								
Vital signs ^{b)}		Xc)		X _d)	X ^{e)}	X ^{e)}	X ^{e)}	X ^{e)}	X ^{c), f)}	X _{c)}
Laboratory tests ^{f)}		X		X		X	X	X	X	X
Antibodies ^{f)}				X ^{g)}		X ^{h)}			X ^{g)}	X ^{g)}
Plasma drug concentration ⁱ⁾					Х	X	Х	Х		
Drug concentration in CSF				X ^{f)}				X ^{j)}		X ^{k)}
HS and DS concentrations in CSF				X ^{f)}				X ^{j)}		X ^{k)}
CSF opening pressure				X ^{f)}				X _{j)}		X ^{k)}
Urinary HS and DS concentrations (including measurement of creatinine for concentration adjustment) ⁽⁾				х		Х	Х	Х	Х	х
Serum HS and DS concentrations ^{f)}				Х		Х	Х	Х	Х	X
Liver and spleen volumes ^{f)}				Х					Х	Х
Cardiac function ^{f)}				Х					Х	Х
Other clinical findings related to neurocognitive and behavioral changes										
12-lead electrocardiogram ^{f)}		Χ							Х	X
Cross-reactive immunologic material ⁱ⁾										—
AEs										—
Concomitant therapies/medications					Х	Х	Х	Х	Х	Х

- of JR-171.
- b) Vital signs: pulse rate, body temperature, blood pressure, respiratory rate, percutaneous oxygen g) saturation and body weight. During the infusion of JR-171, it is necessary to monitor other than body h) Anti-JR-171 antibodies weight (see Section 6.1 and 8.2.3).
- c) Excluding body weight
- d) Only body weight is measured.
- e) Perform before and after administration of JR-171 except for body weight. Body weight will be measured at either measuring point.
- a) Neurocognitive testing and adaptive behavior assessment will be performed before the first infusion f) Perform before administration of JR-171 (or before laronidase at Week 5, for subjects who will receive laronidase after completing the JR-171-101 study)
 - Anti-IDUA and anti-JR-171 antibodies

 - Blood specimens should be collected by following the "PK sampling schedule (plasma drug concentration)".
 - Performed within 5 hours after the end of administration of JR-171

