 - Performed if deemed feasible by the principal investigator or subinvestigator
 - I) Samples will be collected once in Part 1 and obtained before JR-171 administration during the visit.

Part 2

Observation/test timing	Pre-screening	Screening test	Registration	Baseline	Week 1	Week 2	Week 3	Week 4
Visit window	-	Day -28 to Day -7	-	Day -2 to Day 1	Day 1	Day 8 to Day 11 ^{a)} Day 8±3 ^{b)}	Day 15 to Day 18 ^{a)} Day 15±3 ^{b)}	Day 22±3
JR-171 administration					Х	Х	Х	Х
Informed consent	Х							
Subject baseline characteristics ^{c)}		Х						
Assessment based on			Х					
inclusion/exclusion criteria			^					
Allocation for treatment group			X					
Pregnancy testing (female subjects of childbearing potential only)		Х						
Vital signs ^{d)}		X ^{e)}		X ^{f)}	X _{g)}	X _{g)}	X ^{g)}	X _{g)}
Laboratory tests ^{h)}		Х		Х		Х		Х
Antibodies ^{h)}				X ⁱ⁾		X ^{j)}		X _{j)}
Plasma drug concentration b), k)					Х			Х
Drug concentration in CSF				X ^{h)}				
HS and DS concentrations in CSF				X ^{h)}				
CSF opening pressure				X ^{h)}				
Urinary HS and DS concentrations								
(including measurement of creatinine for concentration adjustment) ^{h)}				Х		Х		Х
Serum HS and DS concentrationsh)				Х		Х		Х
Liver and spleen volumesh)				X				
Cardiac functionh)				X				
6-minute walk test ^{m)}				X ^{h)}				
Other clinical findings related to								
neurocognitive and behavioral changes					-			 
12-lead electrocardiogram ^{h)}		X						
BVMT-R and HVLT-R ^{m)}		X _{b)}						
T.O.V.A. m)		X ^{p)}						
PedsQL-FIM ⁿ⁾		X _{p)}			-	-		
Cross-reactive immunologic material ^{o)}								
AEs								
Concomitant therapies/medications					Χ	Х	X	Х

Part 2 cont.

Observation/test timing	Week 5	Week 6	Week 7	Week 8	Week 9	Week 10	Week 11	Week 12	Week 13	Discontinu ation
Visit window	Day 29±3	Day 36±3	Day 43±3	Day 50±3	Day 57±3	Day 64±3	Day 71±3	Day 78±3	Day 85±3	Within 28 days from discontinu ation
JR-171 administration	Х	Х	Х	Χ	Х	Х	X	Х		
Vital signs ^{d)}	X _{g)}	X ^{g)}	X _{g)}	X ^{e), h)}	X ^{e)}					
Laboratory tests ^{h)}		X		Χ		X		X	X	X
Antibodies ^{h)}				X ^{j)}					X ⁱ⁾	X ⁱ⁾
Plasma drug concentration ^{b), k)}								Х		
Drug concentration in CSF								X _{I)}		X ^{m)}
HS and DS concentrations in CSF								X ^{I)}		X ^{m)}
CSF opening pressure								X ^{I)}		X ^{m)}
Urinary HS and DS concentrations (including measurement of creatinine for concentration adjustment) ^{h)}		Х		Х		Х		х	Х	х
Serum HS and DS concentrationsh)		Х		Х		Х		Х	Х	Х

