5.2 Exclusion Criteria

An individual who meets any of the following criteria will be excluded from participation in the JR-171-101 study:

- 1. A patient who has received gene therapy treatment.
- 2. A patient who, in the opinion of the principal investigator or subinvestigator, cannot undergo lumbar puncture, including those who have a difficulty in taking position for lumbar puncture due to joint contracture and those who are likely to develop dyspnea during lumbar puncture.
- 3. A patient who is pregnant or lactating.
- 4. A patient who has developed serious drug allergy or hypersensitivity to any drugs, in the opinion of the principal investigator or subinvestigator, is inappropriate for participation in the study.
- 5. A patient who has received another investigational product within the 12 months prior to enrollment in the study.
- 6. A patient who, in the opinion of the principal investigator or subinvestigator, is ineligible to participate in the study in consideration of patient's safety.

Rationale for the Exclusion Criteria:

- 1. CNS and systemic symptoms could have been alleviated in patients responsive to gene therapy treatment. This criterion was defined to explore the efficacy of JR-171 for CNS and systemic symptoms.
- 2. This criterion was defined due to the necessity of collecting CSF by lumbar puncture to evaluate the efficacy of JR-171 for CNS symptoms.
- 3. This criterion was defined because the safety of reproductive and developmental toxicity as well as genotoxicity have not been proven at the point that JR-171 is administered to patients with MPS I.
- 4. This criterion was defined in consideration of the patient's safety.
- 5. This criterion was defined in consideration of the patient's safety.
- 6. This criterion was defined in consideration of the patient's safety.

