8.3.5 Pregnancy (Female Subjects and Subject's Female Co-partners of Childbearing Potential Only)

- For female subjects, details of all pregnancies in childbearing potential (female subjects of non-childbearing potential are confirmed by being either post-menopausal for more than 1 year prior to the time of informed consent or surgically sterile) will be collected after the start of study intervention and until a miscarriage, an abortion or 1 month after the delivery. The follow-up for infants will be about one month after the birth.
- If a pregnancy is confirmed in a female subject or subject's female co-partner of childbearing potential, the principal investigator should inform the sponsor within 24 hours of learning of the pregnancy using the designated form.
- Abnormal pregnancy outcomes (e.g., spontaneous abortion, fetal death, stillbirth, congenital anomalies, ectopic pregnancy) are considered SAEs.
- For female subjects, whether or not a measurement of pregnancy testing has been performed as well as the sample collection date and results of measurement, if performed, should be recorded in the eCRF.

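### The only scheduled pregnancy test is at screening, 7 to 28 days before the first dose, and no section says to stop JR-171 if a pregnancy is confirmed

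*Combined protocol and SAP*

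**What the plan says.** **Why pregnancy matters here.** Section 5.2 excludes pregnant or lactating patients (criterion 3) on the ground that "the safety of reproductive and developmental toxicity as well as genotoxicity have not been proven".

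**When testing happens.** Section 8.2.1: "Pregnancy testing will be conducted during screening for female subjects of childbearing potential". In both schedules in Section 1.3 the pregnancy row has one mark, in the screening column. There is none at Baseline, at a dosing visit, at the last visit or at discontinuation, and the Part 2 continuation table (Weeks 5 to 13) has no pregnancy row.

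**When eligibility is settled.** The opening of Section 8 says "All screening evaluations must be completed and reviewed to confirm that potential subjects meet all eligibility criteria". The schedules place this assessment at Registration, before Baseline. In Part 2, "Allocation for treatment group" is also done at Registration.

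**What follows a pregnancy.** Under 8.3.5, "the principal investigator should inform the sponsor within 24 hours of learning of the pregnancy using the designated form". Section 10.2.4 likewise asks for reporting and follow-up to outcome. Section 7.2 lists six reasons for which an investigator may withdraw a subject. Anaphylactic shock is named and pregnancy is not. The nearest items are item 3, "When a subject was found to be ineligible after the start of the clinical study", where continuing would compromise safety or study integrity, and the catch-all item 6. Section 7.2 also says "Subjects who are prematurely withdrawn from the study will not be replaced".

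**The concern.** The plan treats fetal exposure as a risk serious enough to bar entry, then checks for it once, at least a week before any drug is given. A pregnancy too early to show at screening, or conceived between screening and Day 1, would not be found by a site that follows the schedule exactly. The same holds for conception during the dosing weeks.

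Two consequences follow. First, weekly infusions could be given before anyone suspects a pregnancy. Baseline also includes CT or MRI of the abdomen (8.5.6) and a lumbar puncture under sedation or general anesthesia, sometimes with fluoroscopy (8.5.2), so a current result would inform those choices as well. Second, when a pregnancy is confirmed, the site has a firm duty to notify but no stated instruction about the next infusion.

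What is at stake is subject safety, not the statistical analysis.

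**Working it through.** The plan gives no figure of its own for the age of the test result, so it is derived from the visit windows in Section 1.3.

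**Convention.** The Part 1 schedule equates Day -28 with 28 days before Day 1. So Day -k is k days before Day 1, and Day d is d - 1 days after it.

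**Formula.** Age of result at a dose = (days from test to Day 1) + (d - 1). Screening contributes 7 to 28 days; a Baseline test would contribute 0 to 2.

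| Dose | Visit window | Age now (screening test) | Age with a Baseline test |
|---|---|---|---|
| First dose | Day 1 | 7 + 0 = 7 to 28 + 0 = 28 | 0 to 2 |
| Part 1 last dose (Week 4) | Day 22 to 25 | 7 + 21 = 28 to 28 + 24 = 52 | 0 + 21 = 21 to 2 + 24 = 26 |
| Part 2 last dose (Week 12) | Day 78±3, i.e. 75 to 81 | 7 + 74 = 81 to 28 + 80 = 108 | 0 + 74 = 74 to 2 + 80 = 82 |

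A Baseline test alone therefore closes the gap before first exposure but does little for late doses in Part 2.

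**Optional repeats in Part 2 at Weeks 4, 8 and 12.** These visits fall 18 to 24, 46 to 52 and 74 to 80 days after Day 1.

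- Baseline to Week 4: 0 + 18 = 18 to 2 + 24 = 26 days, 3 doses.
- Week 4 to Week 8: 46 - 24 = 22 to 52 - 18 = 34 days, 4 doses.
- Week 8 to Week 12: 74 - 52 = 22 to 80 - 46 = 34 days, 4 doses.
- After the Week 12 test: 1 dose. Total 3 + 4 + 4 + 1 = 12.

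With a stop rule, at most 4 doses would fall between tests. A pregnancy too early to show at one test would be found only at the next, so the number of doses after conception could exceed 4.

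**Number of added tests.** Baseline only: 4 + 15 = 19 if every subject were eligible. Adding three repeats in Part 2: 19 + 15 × 3 = 64. Both are approximate ceilings, because Part 2 is planned at approximately 15.

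**Action rule, section by section.**

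- 7.2: withdrawal is at the investigator's discretion, and pregnancy is not listed.
- 8.3.5: notify within 24 hours and follow to outcome; nothing on dosing.
- 10.2.4: report and follow; nothing on dosing.
- Section 8, opening: discuss immediate safety concerns with the sponsor to decide whether to continue; case by case.
- 7.1.1: withdrawal under 7.2 leads to the discontinuation examinations, done as far as possible if the subject agrees. CSF measures are left to the investigator's judgement. Liver and spleen volumes, by CT or MRI, carry no pregnancy exemption. Restarting laronidase is considered after the examinations.

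**The case against.** The plan is not without controls. Effective contraception is an inclusion criterion (5.1) and must continue until one month after the last dose (6.7). Subjects must contact the investigator at once if they suspect pregnancy (6.7). Investigators may order additional tests (10.1.8), and 8.3.5 provides for recording pregnancy-test results. Section 8.5.6 asks the investigator to weigh the subject's condition and radiation exposure when choosing CT or MRI. The number of females of childbearing potential is not given and could be very small.

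All of that stands, and it lowers the risk. It does not detect an unsuspected pregnancy, because each control needs prior suspicion or an investigator's choice. Self-report may also be weaker in Part 2: the requirement that patients can report their own symptoms (5.1, criterion 4) applies to Part 1 only, and Part 2 has the twelve doses.

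A reader might infer that the protocol lets a pregnant subject go on being dosed. The documents do not support that. Item 3 of 7.2 could cover a pregnancy missed at entry, item 6 could cover others, and Section 8 requires discussion with the sponsor. The fault is the absence of an explicit instruction, not permission to continue.

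A reader might also infer that repeat testing at a fixed interval is required. The documents set no interval, so the spacing of repeats is a matter of choice.

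One objection bears on the remedy. A bare rule to discontinue would send a confirmed-pregnant subject into the 7.1.1 examinations, including possible CT, and could hold up the laronidase decision. The remedy therefore needs a carve-out.

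**Conclusion.** The gap is real and should be closed. Exclusion criterion 3 rests on one result that is a week to four weeks old at first exposure and up to 108 days old at the last Part 2 dose, and no section tells the site to stop JR-171 when a pregnancy is confirmed. The Baseline test and the stop rule are the firm part of the recommendation. Repeats during dosing are optional.

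This rests on the visit windows as printed and on the definition of childbearing potential being read biologically. Sections 8.2.1 and 8.3.5 recognise only post-menopausal or surgically sterile females as not of childbearing potential, so on a literal reading premenarchal girls would be tested too. The benefit depends on how many females of childbearing potential remain to be dosed; the synopsis plans enrollment to end in March 2022.

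It would be wrong to infer that the safety, PK or CSF results are compromised. No endpoint, population or test is affected.

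**What to change.** 1. **Baseline test.** In 8.2.1 and both schedules, add a pregnancy test at Baseline (Day -2 to Day 1) for females of childbearing potential, and state that premenarchal girls are not included. Read the result before the first infusion and before any Baseline CT, fluoroscopy or sedation.
2. **Action rule.** Add to 7.2 that a positive test withholds JR-171 until it is promptly confirmed or refuted, and that a confirmed pregnancy discontinues JR-171 with follow-up under 8.3.5. Exempt these subjects from CT, fluoroscopy and lumbar puncture among the 7.1.1 examinations, and do not make the laronidase decision wait for those examinations.
3. **Optional.** Repeat the test before dosing at visits where urine is already collected, for example Weeks 4, 8 and 12 in Part 2. Test before the Week 5 or Week 13 imaging if CT is used.

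**Cost.** The Baseline test is about one per eligible subject, at most about 19 and fewer in practice because young children are not eligible. No visit is added. Urine and blood are already taken at Baseline; that the urine sample suits a pregnancy test is an assumption, since 8.2.1 names neither urine nor serum.

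**Downsides.** The change needs an amendment with IRB approval. A false positive may delay a dose, and once the first dose has been given laronidase is prohibited (6.5.1), so confirmation must be quick. A Part 2 subject who tests positive at Baseline has already been allocated and, if withdrawn, is not replaced, which is a noticeable loss among about 15.
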